The study will take place at OSUWMC. At OSUWMC there are approximately 13,000 hospitalizations with a diagnosis code for diabetes each year and current annual inpatient diabetes consult service and diabetes educator consults are roughly 3000 per year. OSUWMC has implemented a comprehensive, hospital-wide inpatient diabetes program since 2006, including streamlined computerized diabetes related order sets, carbohydrate-based insulin dosing, education, and ongoing review of outcomes. OSUWMC converted to EPIC EHR in 2011 for both inpatient and outpatient electronic medical records. The medical centers MICU has been utilizing Dexcom G6 CGM for COVID-19 patients since May of 2020 and to date has utilized CGM in over 132 critically ill COVID-19 patients. The study will take place in the MICU. The MICU is a 48-bed critical care center and employs 152 staff nurses. Patients will be identified through daily screening of patients and associated glycemic control in the MICU to identify potential participants with hyperglycemia (glucose >250mg/dl) or those currently on IV insulin. In 2019, prior to the COVID-19 pandemic, OSUWMC had 1,065 unique patient admissions in which the patient had a glucose >250mg/dl over the course of their MICU stay. Within the MICU patient population, patients with more severe illness and those with conditions that may interfere with CGM sensor accuracy will be excluded from participation. Full inclusion and exclusion criteria are as follows:

Eligible individuals are:

- 1) adults >18 years old,
- 2) admitted to OSUWMC MICU and

- 3) have hyperglycemia (glucose >250mg/dl) or are currently on IV insulin.

Non-eligible individuals are:

- 7) Current COVID-19 infection,
- 8) Refractory shock (Levophed dose >0.5 mcg/kg/min or equivalent)
- 9) Actively being treated for diabetic ketoacidosis (DKA)
- 10) Actively being treated for hyperosmolar non-ketoacidosis (HONK)
- 11) Pitting edema, anasarca, blue or purple discoloration to left upper extremity
- 12) Treated with high dose acetaminophen (>1 gram Q6 hours)
- 13) Treated with hydroxyurea
- 14) Are pregnant, patients
- 15) Using home insulin pump therapy during hospitalization, or
- 16) Reside in a corrections institution.

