Sample Size Justification. The primary outcome for the power analysis is the percentage of time spent in target (70-180mg/dl). We estimate from previous studies^{13,28} that these values may have a standard deviation as high as 25 percentage points, in which case with 100 patients in each group we will have 80% power to detect a difference of 10 percentage points in time in range (e.g., 65 vs. 75); a moderate effect size of 0.4. If the standard deviation is lower (e.g., 15 as has been true in some studies), we will have greater power (99%) to detect a 10 point difference and are still well powered to detect smaller differences (e.g., 90% power for a 7 point difference). All power calculations assume an alpha of 0.05 and minimal statistical effects of clustering within the hospitals (e.g., unit or nurse level).

C. Detailed study procedures

Recruitment: Critical care clinical research coordinators will screen for preliminary eligibility and forward potential participant names to study team using a secure medical record in-basket process. The study team will determine eligibility. The study team will ask for permission for the patient to be approached. If permission is granted, the study team will verify eligibility and obtain informed consent from the patient or the patient's legally authorized representative. Consent will be obtained prior to research participation and CGM placement. Recruitment is expected at a rate of 5 patients per week over seven months. Our target recruitment will be 100 MICU patients.

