Procedures. Glucose data will be directly transferred from the MICU patients (N=100) to Android mobile phones/Dexcom G6 app which captures and stores glucose values every 5 minutes (up to 288 values/day for 100% CGM wear). CGM data is automatically transferred from phones/Dexcom G6 app to Dexcom Clarity. Individual patient discrete data will be downloads directly from the Clarity site. Historical controls meeting the gateway criteria (glucose >250 mg/dl or on IV insulin during admission) from the same MICU will be matched on the following factors: Diagnosis and type of diabetes, home insulin use, steroid use during hospitalization, vasopressor use, North vs. South MICU wings (NP team floor vs. resident team floor, respectively), and diabetic ketoacidosis (DKA)/hyperosmolar hyperglycemic syndrome (HHS) status. POC glucose values for historical controls (N=100) will be obtained directly from OSUWMC EHR. EHR data will be obtained through an information warehouse request providing time stamped, POC glucose value for each match patient. All data will be uploaded into STATA 15.0 where it will be cleaned and merged prior to analysis.

Variables and Measures. Demographic, admission, and diabetes specific variables of interest appear in Table 2 and will be collected from the EHR for MICU participants and for historical controls. Clinical condition variables will include presence of renal replacement, mechanical ventilation, ECMO, associated cardiac arrest or cerebrovascular accident and SOFA score. SOFA score was calculated, though noted to have limited discriminant function for predicting mortality.³² The SOFA score has been validated in critically ill patients³³, and is currently the scoring system recommended by the Sepsis 3 definition.³⁴ CGM and POC glucose data will be aggregated into glucose ranges and thresholds as described in Table 2.

Exploratory aim:

RQ 4: To assess hospitalization outcomes and conduct economic evaluation of the costs to deliver CGM implementation in the MICU.

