Descriptive statistics of central tendency (range, mean, median, and standard deviation) will describe variable characteristics and examine data distribution for normality and outliers. Descriptive statistics will summarize the sample characteristics and distribution of each variable. Data will be screened for normality, outliers, and homogeneity. Continuous variables with normal distribution will be reported as mean (standard deviation) while non-normal distribution will be reported as median (interquartile range). For **RQ1**, multivariate linear models will be used to evaluate clinical utility and implementation variables while examining the effects of patient condition (i.e., sequential organ failure assessment (SOFA) score, renal replacement, ventilator support, pH) as covariates. For **RQ 2**, For qualitative analysis of focus group data, a code book will be developed a priori based on the semi-structured interview questions. Interview data, fieldnotes and memos were imported into NVivo 12.0 (Doncaster, Australia) for data management and analyzed using a qualitative descriptive approach.^{35,36} Two researchers ([name] and [name]) will perform qualitative analysis. Portions of text will be coded with terms that were low inference (“data close”); then grouped into thematic categories and subthemes.³⁵ For **RQ3**, hyperglycemic and hypoglycemic events will be identified for CGM and non-CGM users. Discrete CGM glucose values will be used to aggregate derived measures of glucose variability, including time in target (blood glucose value of 70-180mg/dl), time 100-180mg/dl (representing a more conservative target used inpatient), time 140-180mg/dl (representing institutions IV insulin guideline glycemic target), time above target (>180mg/dl & >250mg/dl), time in hypoglycemia (<70mg/dl & <55mg/dl), glucose standard deviation, and coefficient of variation. Daily percent time in target as well as cumulative time in target will be assessed. Time in target will be derived from ADA glucose targets defining hypoglycemia as a blood glucose less than 70mg/dl and peak post-prandial glucose as <180mg/dl³⁷. The blood glucose range of 70-180mg/dl is consistent with other studies examining time in target.³⁸⁻⁴¹ Measures of hypoglycemia will be in accordance with ADA recommendations for measurement at <70mg/dl and <55mg/dl which is a marker of severe hypoglycemia.⁴² Days with $\geq 70\%$ CGM percent wear, as recommended by ADA, will be included in daily time in target analysis.⁴² For matched historical control patients, percent POC in target (70-180mg/dl), 100-180mg/dl, 140-180mg/dl, percent POC >180mg/dl and percent POC >250mg/dl, percent POC <70mg/dl and percent POC <55mg/dl will be evaluated consistent with other recent studies.^{43,44} For CGM daily glycemic control (i.e., time in range [70-180mg/dl], time 100-180mg/dl, time 140-180mg/dl), linear mixed effect modeling (LMM) for repeated measures will be used to adjust for between subject and within subject variance. A 3-tiered LMM will be used to control for patient, unit, and nurse specific variability. LMM will be repeated for analysis of daily POC glucose control for matched historical control patients for days with ≥ 3 POC fingersticks performed. Two-sided significance level of 0.05 was used for all the statistical tests. For **RQ4**, the cost analysis for the proposed study will be conducted from the provider perspective. Cost estimation involves three major steps: (1) identify the relevant cost items; (2) measure the use of resources; and (3) place a value on the resources used. We will obtain estimated costs for proposed CGM implementation. Direct benefits and savings tend to fall into one of two categories: either savings from enhanced efficiency and productivity, or savings from outcomes improvement (e.g., reducing length of stay, lower 30 day readmissions). Costs that do not vary with the number of patients will be categorized as fixed costs, whereas those that vary by the number of patients will be defined as variable costs. The costs of the CGM implementation will be compared to costs under a control scenario. We will estimate the potential costs and cost savings resulting from the CGM implementation.

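### RQ3 does not match historical controls on in-hospital IV insulin, or on severity beyond vasopressor use and DKA/HHS status, and states no adjustment for either

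*Combined protocol and SAP*

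**What the plan says.** **Entry.** Under III.B Sample, a MICU adult qualifies if they "have hyperglycemia (glucose >250mg/dl) or are currently on IV insulin". Section III.C, RQ 3 Procedures, applies the same two alternatives to historical controls, but there IV insulin may occur at any time in the admission.

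**Matching.** The same paragraph lists the factors: "Diagnosis and type of diabetes, home insulin use, steroid use during hospitalization, vasopressor use, North vs. South MICU wings", with DKA/HHS status as the sixth. Insulin use at home is on the list; insulin route in hospital is not.

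**Outcomes.** III.D Data Analysis includes among the RQ3 outcomes "time 140-180mg/dl (representing institutions IV insulin guideline glycemic target". The outcome used for power is the wider 70-180 mg/dl range.

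**Adjustment.** III.D names "sequential organ failure assessment (SOFA) score, renal replacement, ventilator support, pH) as covariates", but in the RQ1 sentence only. For RQ3 it describes a three-tiered linear mixed model for patient, unit and nurse variability and says this model is repeated for the controls. For RQ4 it sets out a costing method. It states no comparison model for length of stay, discharge level, readmission, morbidity or mortality.

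**The concern.** RQ3 is a non-randomised comparison with patients from an earlier period, so much of its credibility rests on how alike the two groups are made. Under the stated list, a CGM patient on an insulin infusion can be paired with a control who had one glucose above 250 mg/dl and never received an infusion. The plan itself associates infusion with a specific glucose band that is also an outcome. Likewise, a ventilated patient on dialysis can be paired with a patient on neither, provided vasopressor use and the other listed factors agree.

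If the groups then differ in the share on IV insulin, or in severity, part of any difference in glycemic outcomes reflects case mix. The same applies to the RQ4 hypotheses on mortality, stay and readmission. The distortion could favour CGM or work against it.

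**Working it through.** **Step 1: what is matched, collected and adjusted.**

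| Characteristic | RQ3 matching factor | Data collected | Named as a covariate |
|---|---|---|---|
| In-hospital IV insulin | No | Needed to apply the entry rule; the patient schedule of activities lists total daily insulin dose, not route | Nowhere |
| Vasopressor use | Yes | Yes | Nowhere |
| DKA/HHS status | Yes | Yes | Nowhere |
| SOFA score | No | Yes | RQ1 only |
| Ventilation | No | Yes | RQ1 only |
| Renal replacement | No | Yes | RQ1 only |

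**Step 2: does the mixed model close the gap?** A patient-level variance component accounts for correlation between days in the same patient. It does not remove a difference in average case mix between groups. Repeating the model in controls also gives two separate fits, so no adjusted between-group contrast is defined.

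**Step 3: reproduce the plan's power.** Inputs from the Sample Size Justification: "with 100 patients in each group we will have 80% power to detect a difference of 10 percentage points in time in range" and "these values may have a standard deviation as high as 25 percentage points". Alpha is 0.05, and III.D makes it two-sided: "Two-sided significance level of 0.05 was used for all the statistical tests".

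- Standard error of the difference = SD × √(2/100): 3.54 points at SD 25 and 2.12 at SD 15.
- Power ≈ Φ(difference/SE − 1.96).
- SD 25, difference 10: Φ(2.83 − 1.96) = 80.7% (stated 80%).
- SD 15, difference 10: 99.7% (stated 99%).
- SD 15, difference 7: 91.0% (stated 90%).

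The arithmetic is sound. It assumes that the groups differ systematically only by CGM. The smallest observed difference reaching p < 0.05 is 1.96 × SE, that is 6.9 points at SD 25 and 4.2 points at SD 15.

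**Step 4: illustrate the bias.** Bias in time in range = (difference between groups in share on IV insulin) × (gap in mean time in range between IV insulin and other patients). The documents give neither input, so both are assumed. With no true effect, the two-sided rejection probability is 1 − Φ(1.96 − bias/SE) + Φ(−1.96 − bias/SE).

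| Assumed imbalance | Assumed gap | Bias | False-positive rate, SD 25 | SD 15 |
|---|---|---|---|---|
| 0 | any | 0 | 5.0% | 5.0% |
| 10 points | 10 points | 1 point | 5.9% | 7.6% |
| 20 points | 10 points | 2 points | 8.7% | 15.6% |
| 20 points | 20 points | 4 points | 20.5% | 47.0% |

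For the last row at SD 25: 4/3.54 = 1.13, and 1 − Φ(0.83) + Φ(−3.09) = 0.205.

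**Step 5: the other direction.** A true 10-point gain with a bias of −4 leaves a net 6 points. At SD 25 the power falls from 80.7% to Φ(6/3.54 − 1.96) = 39.6%.

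**Step 6: what adjustment does to power.** Assume half the patients are on IV insulin, a gap of 10 to 20 points and a total SD of 25. The within-stratum SD is √(625 − 0.25 × gap²), which is 24.5 to 22.9. Power for 10 points is then 82% to 87%, so balancing or adjusting for IV insulin loses no power here.

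**The case against.** The strongest reply is that the plan already does a good deal. Controls come from the same MICU under the same two entry criteria, and six factors are matched. Two of these, vasopressor use and DKA/HHS status, bear on acuity. Some of any IV insulin difference will be explained by diabetes type, home insulin, steroids and DKA/HHS status, so matching on those already removes part of it. RQ4 is declared exploratory. All of this stands, and it limits the point in four ways.

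- A reader might infer that severity is not controlled at all. The matching list contradicts that; what is missing is severity beyond the two matched factors.
- A reader might infer that IV insulin defines eligibility and the primary glucose target. It is one of two alternative routes. The plan ties it to 140-180 mg/dl, not to the powered 70-180 mg/dl range, and does not say what target applies to other patients.
- A reader might infer a bias as large as the planned 10-point effect. That needs, for example, a 40-point imbalance remaining after matching and a 25-point gap (0.40 × 25 = 10). Nothing in the documents supports either figure, and the mildest case in the table is close to nominal.
- A reader might infer that controls will be sicker, which would favour CGM, because the exclusions are written for participants and only the entry criteria are stated for controls. The documents do not say whether the exclusions will be applied to controls, so the direction cannot be settled.

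One could also say that collecting SOFA and organ support under Aim 3 implies adjustment. No such use is stated, whereas the RQ1 sentence names its covariates.

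**Conclusion.** The omission is clear from the text. In-hospital IV insulin is neither matched nor adjusted for, and SOFA, ventilation and renal replacement are collected but have no stated role in the RQ3 or RQ4 comparisons. Residual imbalance in these can therefore create or mask an apparent CGM effect.

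The size is unknown. The false-positive rates of about 6% to 47% come from assumed biases of 1 to 4 points in a simple two-sample comparison of 100 against 100. They show that a modest imbalance may matter, not that one exists. The sample size calculation is not at fault. The point carries most weight for RQ3 and less for the exploratory RQ4. It is worth correcting before controls are drawn.

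**What to change.** 1. Define an index time for controls that is comparable to CGM start, for example the first time the entry criterion is met in the MICU. Add IV insulin at index (yes/no) as a matching factor, or as a covariate if the matched cells become too thin.
2. Replace the two separate RQ3 models with one joint model for both groups. Include a group term and adjust for IV insulin, SOFA, ventilation and renal replacement measured at or before index. Later daily values should not be used, because CGM may have influenced them.
3. Use the same covariates for the exploratory RQ4 clinical outcomes, and report covariate balance between groups.

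The cost is a little more EHR extraction and analysis, and possibly looser matching on other factors. IV insulin status is already needed to apply the entry rule to controls, and the severity variables are already planned. The 1,065 MICU admissions with glucose above 250 mg/dl in 2019 are about 10.7 per required control (1,065/100). That count precedes exclusions and six-factor matching and does not count patients who qualify by IV insulin alone, so it shows only that the pool is probably adequate.

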Sustained use	
Revert from Q4 hour to Q1 hour POC testing if:
 
 1) CGM >20% difference from the POC when the glucose is >100 mg/dl 2) CGM >20 mg/dl difference from the POC when the glucose is <100 mg/dl 3) Revert back to Q4 hour POC testing when two consecutive sensor-meter pairs approximately 1-hour apart meet the initial validation criteria 
Revert from Q4 hour to Q2 hour POC testing for a duration of 6 hours for one of the following clinical status events occurring in isolation:
 
 4) Intubation 5) Pressor support initiated (Levophed dose <0.5 mcg/kg/min or equivalent) 6) New cardiovascular event (MI, CVA) 7) Initiation or discontinuation of nutrition support (i.e., enteral feed, total parenteral nutrition) 8) Hemoglobin <7g/dL 9) CGM or POC glucose <70mg/dl (follow OSUWMC hypoglycemia policy for initial treatment and monitoring) 10) Predicted low alert (glucose predicted to be <55mg/dl in the following 20 minutes) 11) Acidosis with pH <7.3 12) Signs and symptoms do not match glucose readings, particularly for hypoglycemia 
Revert from Q4 hour to Q1 hour POC testing for a duration of 6 hours for two or more of the above clinical status events occurring together (example: patient is intubated and starts pressor support)
 
If after 6 hours no additional clinical scenarios featured above have developed than Q4 hour POC testing can resume after initial validation using two consecutive sensor-meter pairs.
 
Obtain 1 time POC glucose if:
 
 13) No glucose value appears on android screen (due to signal loss, Low/High measure) 14) Low threshold alert (<100mg/dl)
Stop CGM use	
Stop use of CGM for insulin titration or glucose monitoring and revert from Q4 hour to Q1 hour POC testing (do not remove CGM sensor until sensor expires) for the following conditions:
 
 1) Refractory shock (Levophed dose >0.5 mcg/kg/min or equivalent) 2) Cardiac arrest 3) Newly developed diabetic ketoacidosis (DKA) (pH <7.3 or serum bicarbonate <15 mEq/L in the setting of elevated ketones) 4) Newly developed hyperosmolar non-ketoacidosis (HONK) 5) Pitting edema, anasarca, blue or purple discoloration to bilateral upper extremity 6) Initiation of treatment with high dose acetaminophen (>1 gram Q6 hours) 
Initiation of treatment with hydroxyurea

III. Procedures

A. Research Design

Hybrid Research Design

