		Proportion of patients approached to received GCM monitoring/number of patients eligible to receive initial CGM monitoring	Admission		
		Acceptability of CGM			
		Appropriateness of CGM			
		Feasibility of CGM			
		CGM knowledge			
Aim 3	Patient condition	Demographic data: Age, race/ethnicity, gender	Admission	
 • EHR 	
		Height, weight, and BMI	Admission		
		Diagnosis and type of diabetes	Admission		
		Home diabetes regimen	Admission		
		Total daily insulin dose	Daily		
		Past medical history: tobacco use, COPD, hypertension, heart failure, coronary artery disease	Admission		
		Clinical condition: Admission/inpatient glucose, HbA1c, admission diagnosis, admitting service, MICU	Admission		

		location (North vs. South), DKA/HHS, sepsis, acute liver failure, acute heart failure		
		Clinical condition: SOFA score, dialysis, thromboembolic events, ECMO mechanical ventilation, ICU/hospital length of stay, cardiac arrest, cerebrovascular accident, mortality	Daily	
		Medications: vasopressor use, steroids, anticoagulants, acetaminophen dose	Daily	
		Creatinine, eGFR, ALT, AST, TBR, WBC, procalcitonin, ferritin, CRP, IL6, D-dimer, PTT, INR, troponin, pH, BHB, bicarbonate	Daily	
		Enteral or parenteral nutrition	Daily	
		O2 sat, pAO2, blood pressure	Daily	
Aim 3	Glycemic control	Time in target for CGM patients (70-180mg/dl)	Daily	
 • Clarity • EHR
		Time 100-180mg/dl for CGM patients	Daily	
		Time 140-180mg/dl for CGM patients	Daily	
		Time above range for CGM patients (>180mg/dl & >250mg/dl)	Daily	
		Time in hypoglycemia for CGM patients (<70mg/dl & <55mg/dl)	Daily	
		Percent POC in target (70-180mg/dl) (matched controls)	Daily	
		Percent POC 100-180mg/dl (matched controls)	Daily	
		Percent POC 140-180mg/dl (matched controls)	Daily	
		Percent POC above range (>180mg/dl & >250mg/dl) (matched controls)	Daily	
		Percent POC in hypoglycemia (<70mg/dl & <55mg/dl) (matched controls)	Daily	
		Glucose standard deviation	Daily	
		Glucose coefficient of variation	Daily	
Aim 4	Hospitalization outcomes and costs	Length of stay [ICU, total stay]	Discharge	
 • EHR • Clarity download
		Cost of stay	Discharge	
		Discharge level of care [home, SNF]	Discharge	
		Morbidity	Discharge	
		Mortality	Discharge	
		Readmission rate [30 days]	30d s/p discharge	
		Cost of CGM vs. standard POC glucose monitoring materials.	Discharge	

Table 3. Nurse Participant Schedule of Activities

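### Controls are matched on whole-stay steroid use and undated vasopressor use, with no control index day, so matched flags do not ensure equal exposure on the glucose days compared

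*Combined protocol and SAP*

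**What the plan says.** Section III.C, RQ 3 Procedures, lists the matching factors, among them "home insulin use, steroid use during hospitalization, vasopressor use, North vs. South MICU wings". Steroids carry a window, the hospitalization. Vasopressors carry none. Controls qualify through a glucose above 250 mg/dl or IV insulin at some point in the admission, and no index day is defined for them.

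CGM patients do have a natural start. The sensor goes on after consent, and monitoring continues until the hospital stay ends (RQ 1 Procedures). Table 1, under sustained use, lists "Pressor support initiated (Levophed dose <0.5 mcg/kg/min or equivalent") among the events that can arise while CGM is in use.

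The outcome is daily. Section III.D keeps days with at least 70% wear for CGM and days with at least 3 fingersticks for controls. It describes a mixed model for the CGM patients with levels for patient, unit and nurse, then repeats the modelling for controls. The covariates it names (SOFA, renal replacement, ventilation, pH) belong to RQ1 and include neither drug.

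The Aim 3 rows of Table 2 (Patient Participant Schedule of Activities) include "Medications: vasopressor use, steroids, anticoagulants, acetaminophen dose", to be recorded daily. RQ 3 Variables and Measures says that Table 2 variables are taken from the EHR for participants and controls alike.

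**The concern.** By choosing steroids and vasopressors as matching factors, the sponsor already treats them as related to glucose. Matching is useful only if it balances exposure when the outcome is measured. A whole-stay flag does not do that. A CGM patient on steroids on every monitored day can be paired with a control whose steroids fell only on days with too few fingersticks to be analysed. The pair looks balanced, but its analysed days are not. Time in range can then differ between the groups with no CGM effect, or a real effect can be hidden.

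The steroid flag also uses information from after sensor placement, so controls are chosen partly on what happened during follow-up. RQ4 compares length of stay with matched controls. Patients who stay longer have more days on which a first dose can occur, so matching on ever-use partly matches on the outcome.

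**Working it through.** **1. The plan's own figures.** The Sample Size Justification states: "The primary outcome for the power analysis is the percentage of time spent in target (70-180mg/dl"). It says that "these values may have a standard deviation as high as 25 percentage points" and that "with 100 patients in each group we will have 80% power to detect a difference of 10 percentage points in time in range". On alpha it says: "All power calculations assume an alpha of 0.05 and minimal statistical effects of clustering within the hospitals". Section III.D adds: "Two-sided significance level of 0.05 was used for all the statistical tests".

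SE = SD × √(2/100), which is 3.54 for SD 25 and 2.12 for SD 15. Power ≈ Φ(difference/SE − 1.96).

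| Difference | SD | Plan | Normal approximation | Noncentral t, 198 df |
|---|---|---|---|---|
| 10 | 25 | 80% | 80.7% | 80.4% |
| 10 | 15 | 99% | 99.7% | 99.7% |
| 7 | 15 | 90% | 91.0% | 90.7% |

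The stated power reproduces. It does not depend on the matching factors, so it neither supports nor weakens the point.

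**2. The windows side by side.**

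| Item | Window in the plan |
|---|---|
| Steroid match | whole hospitalization |
| Vasopressor match | none stated |
| Control entry | any time in the admission |
| CGM monitoring | placement to end of stay |
| Outcome days, CGM | at least 70% wear |
| Outcome days, controls | at least 3 fingersticks |
| Drug data | daily |

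The matching window and the outcome days can differ in three ways: days before placement, days dropped by the wear or fingerstick rule, and control days with no index time to anchor them.

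**3. Illustrative size.** The documents give neither a steroid effect on time in range nor an exposure gap, so every input below is an assumption. Take one drug, with flags perfectly matched. Then

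bias = share of patients flagged × gap in share of analysed days exposed × loss in time in range on an exposed day.

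The assumed ranges are 25% to 74%, 10 to 40 percentage points, and 10 to 20 points. The 74% is the share on steroids at placement in the earlier COVID-19 cohort (Section II). This study excludes current COVID-19, so that figure serves only as an upper case.

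- Low: 0.25 × 0.10 × 10 = 0.25 points
- Middle: 0.50 × 0.20 × 20 = 2.0 points
- High: 0.74 × 0.40 × 20 = 5.92 points

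**4. Consequences.** With no CGM effect, two-sided rejection = Φ(bias/SE − 1.96) + Φ(−bias/SE − 1.96). If the bias runs against CGM, power for a true 10-point gain is the power for (10 − bias).

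| Bias | Rejection, SD 25 | Rejection, SD 15 | Power for 10 points if bias is against CGM, SD 25 |
|---|---|---|---|
| 0.25 | 5.1% | 5.2% | 78.7% |
| 2.0 | 8.7% | 15.6% | 61.9% |
| 5.92 | 38.8% | 79.7% | 21.0% |

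For the middle case with SD 25: 2.0/3.54 = 0.57, and Φ(−1.39) + Φ(−2.53) ≈ 0.087. As in the plan's power calculation, the groups are treated as independent with no clustering effect.

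**The case against.** The strongest case on the other side has five parts.

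- *Overlap.* CGM runs to the end of the stay, so in that group the whole-stay window largely coincides with the monitored days. This stands and narrows the point. What remains is time before placement, excluded days and the missing control index day.
- *Vasopressors.* A reader might infer that both drugs are matched on whole-stay flags. The documents say so only for steroids. For vasopressors the defect is an undefined window. Because Table 1 treats pressor initiation as an on-study event, a reading that counts any use would take in events after placement, but it is only one reading.
- *Silence is not exclusion.* A reader might infer that the sponsor decided to leave both drugs out of the RQ3 model. Section III.D names no clinical covariates for RQ3, which is under-specification. Even so, nothing in the plan as written corrects the imbalance.
- *Size and direction.* An 80% against 40% share of exposed days with a 10-point effect gives 0.40 × 10 = 4 points, and it is tempting to set that against the planned 10-point difference. But the gap has no source, and the 4 points apply only within steroid pairs. If half the pairs were steroid pairs, the overall bias would be 2 points. More steroid days in the CGM group would lower its time in range, against the study hypothesis; the reverse gap would favour CGM. The documents give no reason to expect either, and without a systematic gap the misalignment is mainly noise.
- *Adjusting for later exposure.* Daily drug values after placement could themselves be affected by CGM-guided care. This stands and shapes the fix.

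RQ4 is labelled exploratory, so its part of the point is secondary.

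**Conclusion.** The point holds in a limited form. The steroid match uses the whole stay, the vasopressor match has no window, and controls have no index day. Equal flags therefore do not ensure equal exposure on the days compared, and no stated analysis repairs this although daily data are planned. For RQ4 the steroid match also conditions in part on length of stay.

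The size and direction of bias cannot be derived from the documents. Under the assumed ranges it is 0.25 to 5.9 points overall, from negligible to more than half of the planned 10-point difference (5.92/10 = 59%). The middle case of 2 points is enough to raise false rejection to 8.7% or 15.6%. A claim that the design will produce a false CGM benefit, or a bias of any particular size, goes beyond the documents. The correction is worth making before controls are selected, because it is specific and inexpensive. The sample size needs no change on this account.

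**What to change.** 1. Define an index time in both groups: sensor placement for CGM patients, and the corresponding qualifying time for controls.
2. Match on steroid and vasopressor status in a stated window at or before that time, for example the prior 24 hours, in place of the whole-stay and undated factors. Use the same matched set for RQ4.
3. Fit one pooled RQ3 mixed model with a group term, and enter daily steroid and vasopressor exposure as day-level covariates. Adding these terms to separate models for each group would not adjust the comparison.
4. Report the pooled model also without the daily terms as a sensitivity analysis, because exposure after placement, especially to vasopressors, might be affected by CGM-guided care.

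The cost is SAP wording, an index-time rule for controls, a pooled model and two extra terms. No new data are needed, provided the daily medication row of Table 2 is extracted for controls as well as participants, as RQ 3 Variables and Measures indicates.
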